As noted, the primary trial analysis will focus on YP within ‘Analysis Arms’ 1 and 2 (that is, pure intervention and pure control). Young people in Arms 3 and 4 will be excluded from the primary analysis. Arms 3 and 4 will however be included in an exploratory analysis, where the impact of just one of the two YPSWs/SSWs being assigned to the intervention is estimated. This is described in the final section ‘Analysis of all four arms of the trial’.

The randomisation method aims to maximise the sample size for the primary analysis. Each SSW was assigned to a ‘unique YPSW’ prior to the start of the trial, with this being done by assigning each SSW to the YPSW with whom they share the most eligible YP. To illustrate, if a SSW has 10 eligible YP, and for five of the 10 they work alongside YPSW-1, for three they work with YPSW-2, and for two they work with YPSW-3, then this SSW is assigned to YPSW-1.⁵ If YPSW-1 is then randomly allocated to the intervention group, this SSW will also be assigned to the intervention group (and vice versa). Note that two or more SSWs might be assigned to a single YPSW under this model. The aim in doing this assigning is to generate a set of YPSW/SSW ‘clusters’ that between them cover as many eligible YP as possible. The randomisation steps are described in detail in the Appendix.

The steps in the randomisation are summarised below:

Step 1	Assign each SSW to a unique YPSW (the one they work with for most YP)
Step 2	Randomly allocate YPSW to either intervention and control
Step 3	Assign each SSW to ‘intervention’ or ‘control’ with the allocation being the same as the allocation to group of their ‘unique YPSW’
Step 4	Having determined the group status for every YPSW and SSW, establish which of four arms each YP now belongs to:

⁵ With assignment to an SSW being done randomly if there are two or more SSWs with which they share the same number of families.

	
Arm 1 : Both of the YP's SSW and YPSW assigned to intervention;
 
Arm 2 : Both of the YP's SSW and YPSW assigned to control;
 
Arm 3: The YP's SSW assigned to intervention but their YPSW assigned to control
 
Arm 4: The YP's SSW assigned to control but their YPSW assigned to intervention.
 
Only those in Arms 1 and 2 are used in the primary analysis.

--	---

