This approach to randomisation does not give a four-arm RCT with balance across all four arms. Analysis Arms 1 and 2 will be balanced (which is vital for the primary analysis), and Arms 3 and 4 will be balanced, but the YP in Arms 3 and 4 will have different experiences to those in Arms 1 and 2 in the sense that the Arms 3 and 4 YP will be more likely to have a YPSW and SSW who work together infrequently. This does not affect the primary analysis, which compares just Arms 1 and 2, but in the exploratory analysis that compares all four arms the lack of balance will be acknowledged.

Once randomisation has been completed, each young person will have been assigned to one of the four randomisation arms. Some contamination during the trial is inevitable (with some 'control' YP being assigned to a trained social worker during the trial and vice versa). This will be monitored and sensitivity analysis will be conducted to establish the degree to which this dilutes the overall effect sizes (see analysis section).

Sample size calculations overview

Our primary analysis (which uses externalising behaviour as measured through the SDQ as an outcome) focuses on the YP where both the YPSW and SSW have either been assigned to the intervention group or to the control group (Analysis Arms 1 and 2 as described in the randomisation section above). Arms 1 and 2 between them cover 66% of all the eligible YP identified as in-scope for the trial.

Table 2 sets out the MDES and sample sizes that were originally anticipated and as they were presented in version 1 of the trial protocol. The final column sets out our revised estimates after recruitment of LAs, baseline data collection, and randomisation. The original intention was to recruit 10 LAs to the trial rather than the eight achieved, and the initial predictions of response rate at baseline proved too optimistic. However, the number of social workers was much larger than anticipated, which reduces the average cluster size. Nevertheless, the MDES

has increased from the initial protocol estimate of 0.21 standard deviations to 0.24 standard deviations.

The assumptions behind the calculations are:

- Across the eight LAs, the total number of eligible YP is 1,477. Of these, 979 have been assigned to one of the two primary analysis arms: 458 to the group where both the YPSW and the SSW are assigned to the intervention group and 521 to the group where both the YPSW and the SSW are assigned to the control group.

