An exploratory analysis for the primary and secondary outcomes will include Analysis Arms 3 and 4 in the regression model, that is the groups of YP where one social worker (YPSW or SSW) was randomised to training and the other to control. For this analysis the trial will be assumed to follow a factorial design. The regressions for this analysis will generate three effect estimates: the effect of the intervention being delivered to SSWs; the effect of the intervention being delivered to YPSWs; and the additive effect of the intervention being delivered jointly to SSWs and YPSWs (that is, the interaction effect). Differences between the effect sizes will be tested for significance, but given the relatively small sample sizes in Arms 3 and 4 we do not anticipate they will reach significance, so the results will be presented purely descriptively. Given that Arms 3 and 4 are not balanced with Arms 1 and 2 (see randomisation section), this analysis will be presented with suitable caveats, and the fact that the effect sizes may be biased, will be explained.

The model for this analysis is:

$$Y_{ijk} = \beta_0 + \beta_1 Z_{1ik} + \beta_2 Z_{2ik} + \beta_3 Z_{1ik} Z_{2ik} + \beta_4 X_{ijk} + \beta_5 LA_k + u_{ijk} + \varepsilon_{ijk} \quad (\text{Eq 4})$$

where

Y_{ijk} = outcome score at follow-up for young person i assigned at baseline to YPSW j within LA k;

$\beta_0, \beta_1, \beta_2, \beta_3, \beta_4, \beta_5$ = fixed effect parameters;

Z_{1ik} = indicator variable for allocation of the YP's YPSW (0=control; 1=intervention) within LA k;

Z_{2ik} = indicator variable for allocation of the YP's SSW (0=control; 1=intervention) within LA k;

X_{ijk} = baseline externalising score for young person i assigned at baseline to YPSW j within LA k;

LA_k = a vector for the local authority dummy variables, of which there will be seven. β_3 is a coefficient vector for the LA dummy covariates;

u_{ij} = random effect for ith member of YPSW j;

ε_{ijk} = residual error term for ith member of cluster j.

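### The exploratory four-arm analysis labels the interaction term as the effect of joint delivery, leaves the both-versus-one contrasts unspecified, and mixes young people who could never have entered Arms 3 or 4 with those who could

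*SAP*

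**What the plan says.** In the SAP section on the analysis of all four arms, a factorial-type model is planned for the primary and secondary outcomes. "The regressions for this analysis will generate three effect estimates": one for delivery to SSWs, one for delivery to YPSWs, and "the additive effect of the intervention being delivered jointly to SSWs and YPSWs (that is, the interaction effect"). Eq 4 contains Z1 (YPSW allocation), Z2 (SSW allocation) and their product, each indicator coded "0=control; 1=intervention) within LA k". The section goes on: "Differences between the effect sizes will be tested for significance". It names no pairs. It does not expect significance, "so the results will be presented purely descriptively". The Eq 4 legend describes beta3 as the coefficient vector for the LA dummies, although in the equation the LA coefficient is beta5 and beta3 multiplies Z1Z2.

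On comparability, the Randomisation section states: "This approach to randomisation does not give a four-arm RCT with balance across all four arms". It attributes this to young people (YP) in Arms 3 and 4 more often having workers who rarely work together. The SAP deals with it through caveats and an explanation that the effect sizes may be biased.

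**The concern.** Eq 4 is the only planned model that can show whether training both workers does more than training one. A report that follows the wording would present beta3 on the line for joint delivery. Beta3 is zero when the two benefits simply add, and has the opposite sign to the benefits when they overlap. A test of beta3 against beta1 or beta2, which the unspecified wording permits, would not answer the both-versus-one question either.

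The second part concerns bias. The SAP's imbalance has an identifiable source that is fixed before randomisation. It can therefore be removed by restriction or modelling, not only disclosed.

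**Working it through.** **1. Meaning of the Eq 4 coefficients.** With 0/1 indicators, the cell means relative to neither worker trained, at fixed baseline score and LA, are:

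- YPSW only (Arm 4): beta1
- SSW only (Arm 3): beta2
- both (Arm 1): beta1+beta2+beta3

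So both minus YPSW-only is beta2+beta3, and both minus SSW-only is beta1+beta3. Beta3 equals the joint effect only when beta1+beta2 = 0.

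**2. Illustrations** (effect sizes assumed; a lower externalising score is better):

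| Case | beta1 | beta2 | beta3 | Both vs neither | Both vs YPSW only | beta3 - beta1 |
|---|---|---|---|---|---|---|
| Effects add | -0.12 | -0.12 | 0.00 | -0.24 | -0.12 | +0.12 |
| One worker suffices | -0.24 | -0.24 | +0.24 | -0.24 | 0.00 | +0.48 |
| Synergy | -0.12 | -0.12 | -0.12 | -0.36 | -0.24 | 0.00 |

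In the first case beta3 shows nothing although joint delivery works. In the second it looks harmful. In the third, beta3 - beta1 is zero although both workers clearly beat one.

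**3. Precision when all YP are used.** The SAP's MDES formula with n1 = 183, n2 = 208, m = 1.5, ICC 0.2 and R = 0.6 gives 2.8 × sqrt((1/183 + 1/208) × 1.1 × 0.64) = 0.238, which matches the stated 0.24 sd. No figure is given for Eq 4. Arms 3 and 4 hold 1,477 - 979 = 498 eligible YP. Assuming the primary arms' 57% and 70% rates apply to them, 498 × 0.57 × 0.70 is about 199 analysed. Split evenly, the MDES is:

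- beta3: 2.8 × sqrt(0.704 × (1/183 + 1/208 + 1/100 + 1/99)) = 0.41 sd (0.45 if the split is 50/149)
- both versus one: 2.8 × sqrt(0.704 × (1/183 + 1/99)) = 0.29 sd

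**4. Source of the imbalance.** By Steps 1 to 3 of the randomisation, an SSW takes the allocation of their unique YPSW. A YP whose own YPSW is that person (call this matched) can fall only in Arm 1 or Arm 2. For every other YP, the two allocations come from two different YPSWs randomised in the same LA, so all four arms are possible and, within LA, comparable at allocation.

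The appendix illustration agrees. The column maxima sum to 3+1+2+3+1+2+1+1+2+3 = 19 matched YP, leaving 46 - 19 = 27 unmatched. Arms 3 and 4 hold 3 + 12 = 15 YP, all among the 27. The other 12 are in Arms 1 and 2, and 19 + 12 = 31 = 11 + 20.

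**5. Size in the trial.** With p = 198/422 = 0.469 and one common p, an unmatched YP falls in Arm 3 or 4 with probability 2p(1-p) = 0.498. Unmatched eligible YP number about 498/0.498 = 1,000. The SAP sets p by LA, up to 0.70; at p = 0.70 throughout, the figure is 498/0.42, or about 1,190. At p = 0.469, matched YP number about 1,477 - 1,000 = 477, or 477/979 = 49% of Arms 1 and 2 and 0% of Arms 3 and 4.

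If matched YP differ from unmatched YP by d in adjusted follow-up score, and the 49% holds in each of Arms 1 and 2, then beta1 and beta2 each shift by about -0.49d and beta3 by about +0.98d. The documents give no value for d.

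**6. Precision of the restricted run.** About 1,000 × 0.57 × 0.70 = 399 YP would be analysed: about 88 with both workers trained (p²), 112 with neither ((1-p)²), and 99 in each mixed arm. The MDES is:

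- both versus one: 2.8 × sqrt(0.704 × (1/88 + 1/99)) = 0.34 sd
- beta3: 2.8 × sqrt(0.704 × (1/88 + 1/112 + 2/99)) = 0.47 sd

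**The case against.** The strongest reply is that the joint effect is already headlined elsewhere: "the primary trial analysis will focus on YP within ‘Analysis Arms’ 1 and 2 (that is, pure intervention and pure control"). A reader might infer from the label that the trial would report no joint effect, or the reverse of what its data show. The documents do not support that. In the additive example the report would lead with the -0.24 sd from Arm 1 against Arm 2, the third estimate is identified in parentheses as an interaction, and the equation is printed. What remains is that the primary analysis gives both versus neither, whereas both versus one can come only from Eq 4.

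The word additive may have been meant as additional. Beta3 is then the right term for the excess over the sum of the single effects, and Eq 4 needs no change. The wording still says something else and needs correcting.

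A reader might also infer that the SAP commits to testing beta3 against the single-worker effects. It names no pairs, and a test of YPSW-only against SSW-only would also fit the text. The fair criticism is that the contrasts are unspecified.

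The analysis is exploratory, descriptive and openly caveated, and no primary or multiplicity-corrected test rests on it. That limits the weight of the point. The caveats, however, cover imbalance and sample size, not the meaning of beta3.

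On the imbalance, the SAP discloses it and contradicts nothing by leaving it as a caveat. The restricted run has real limits: it is smaller, could not reliably detect a 0.12 sd difference, and describes YP whose workers share fewer cases. The indicator version recovers little sample, because once matched YP have their own intercept and joint effect they add almost nothing to beta1, beta2 or beta3.

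**Conclusion.** The point holds as one of labelling and specification, with an avoidable bias, in an exploratory analysis. The algebra is exact and does not depend on the illustrative effect sizes. That matched YP can fall only in Arms 1 or 2 follows directly from the randomisation steps. The size of the resulting bias is unknown because d is unknown.

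The count of about 1,000 unmatched YP refers to eligible, not analysed, YP and assumes one common allocation fraction (up to about 1,190 at p = 0.70). The figure of about 400 analysed also assumes that the 57% and 70% rates apply to all unmatched YP. Comparability of the four arms holds only within LA and at allocation; differential attrition could still disturb it. The primary analysis does not use Eq 4 and is unaffected.

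**What to change.** In the section on all four arms:

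- Call beta3 the departure from additivity (on the log-odds scale for the binary outcomes).
- Report beta1, beta2 and beta1+beta2+beta3, each against neither worker trained, with confidence intervals.
- Specify beta2+beta3 and beta1+beta3 as the both-versus-one contrasts, and state which differences will be tested. Do not test beta3 against beta1 or beta2.
- Correct the Eq 4 legend: the LA coefficient vector is beta5.
- Add a run of Eq 4 restricted to unmatched YP, or include the matched indicator and its interaction with joint allocation. Keep the LA terms in either case, and say that the results apply to YP whose workers share fewer cases.

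The cost is wording and linear contrasts from a model already planned. Matched status is known from Step 1 of the randomisation, so no new data are needed. The price of the restricted run is precision: the both-versus-one MDES goes from about 0.29 sd with all YP to about 0.34 sd, so it should be presented descriptively, as the SAP already intends for this analysis.

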	measure (instrument, scale, source)	
Young person: SDQ, carer-report version; Child conviction or subject to youth caution (SSDA903 2023-2024); transition into residential care (SSDA903 2023-2024); unplanned moves (SSDA903 2023-2024); missing from care episodes (SSDA903 2023-2024)
 
SSW / YPSW: ARTIC Scale prior to randomisation
 
FCs: Professional Quality of Life Scale (self-report); bespoke questionnaire (self-report) as close as possible to randomisation of YPSW

Randomisation

There are constraints on the number of training places per LA⁴, so YPSWs per LA have not typically been allocated to intervention and control group in the ratio 50:50. Instead, the percentage allocated to the intervention was set so that all available places were filled, with up to a maximum of 70% being allocated to the intervention. In practice, for most LAs, the percentage allocated to the intervention was around 46%. Randomisation was run separately per LA by the trial statistician, giving implicit stratification by LA. Since the trial statistician is undertaking the randomisation and will conduct the statistical analysis, the analysis will not be blind to allocation.

A significant complication in this trial is that the primary analysis aims to test whether delivering the intervention to both SSWs and YPSWs improves outcomes for YP, rather than simply testing whether delivering the intervention to one set of professionals or the other has an impact. Yet, SSWs do not cluster within YPSWs (or vice versa), so straightforward randomisation of YPSW/SSW pairs is not feasible. Inevitably some young people in each LA will have a SSW who has been assigned to the intervention group and a YPSW who has been assigned to the control group, and vice versa. That is, when the randomisation is complete, there will be YP in each of four arms, with the first two (in bold) being the primary analysis arms:

⁴ Depending on the number of in-scope social workers in an LA, either one or two training groups were allocated to the LA, with the maximum number of places per group being 35.

Arm 1: T_{SSW}T_{YPSW} (i.e. both SSW and YPSW assigned to the intervention);

Arm 2: C_{SSW}C_{YPSW} (i.e. both SSW and YPSW assigned to the control group);

Arm 3: T_{SSW}C_{YPSW} (i.e. SSW assigned to the intervention and YPSW assigned to the control group);

Arm 4: C_{SSW}T_{YPSW} (i.e. SSW assigned to the control group and YPSW assigned to the intervention group).

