The analysis of the efficacy trial data will be on an intention-to-treat basis. Estimates of impact per outcome will be based on a multilevel linear regression model with two levels, YPSW and YP, with the baseline version of each outcome being entered as a covariate. LA will be entered as a fixed effect. The analysis will be conducted in SPSS v28.0.1.1 via the MIXED procedure.

If, after non-response, we have data that is essentially unclustered then a single-level model will be fitted.

Primary outcome analysis

The primary outcome measure for YP in the trial is the SDQ externalising score.

The SDQ questionnaire includes five subscales, each with five items, that measure: 1. Emotional symptoms; 2. Conduct problems; 3. Hyperactivity/inattention; 4. Peer problems; 5. Prosocial behaviour. FCs score from 0 to 2 on each item using a scale 'not true', 'somewhat true' or 'certainly true', thus producing a score for each subscale from 0 to 10, where a lower total score is a better outcome for subscales 1-4, and the reverse for subscale 5 (prosocial behaviour). The 'externalising' score (from 0 to 20), is generated by summing the scores of the conduct and hyperactivity subscales.

The calculation of the externalising score will follow the standard SDQ scoring rules. The score will only be calculated where both subscales have a valid score (that is, at least three of the five items have been answered), others being set to missing. Each subscale will be calculated as (total subscale score)*5/(number answered).

The main regression model specification is as follows:

$$Y_{ijk} = \beta_0 + \beta_1 \text{Group}_{jk} + \beta_2 X_{ijk} + \beta_3 LA_k + u_{ijk} + \varepsilon_{ijk} \quad (\text{Eq 1})$$

where

Y_{ijk} = externalising score at follow-up for young person i belonging to assigned at baseline to YPSW j within LA k;

$\beta_0, \beta_1, \beta_2, \beta_3$ = fixed effect parameters;

Group_{jk} = indicator variable for group allocation of the YP's YPSW and SSW (0=control; 1=intervention) within LA k;

X_{ijk} = baseline externalising score for young person i assigned at baseline to YPSW j within LA k;

LA_k = a vector for the local authority dummy variables, of which there will be seven. β_3 is a coefficient vector for the LA dummy covariates;

u_{ij} =random effect for i th member of YPSW j ;

ε_{ijk} = residual error term for i th member of cluster j .

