If, at the analysis stage, the average cluster size proves to be very close to one (that is 1.1 or below) we will use a single-level model rather than two-level. In this case the model will be:

$$Y_{ik} = \beta_0 + \beta_1 Group_{ik} + \beta_2 X_{ik} + \beta_3 LA_k + \varepsilon_{ik} \quad (\text{Eq 2})$$

where

Y_{ik} =externalising score at follow-up for young person i within LA k ;

$\beta_0, \beta_1, \beta_2, \beta_3$ = fixed effect parameters;

$Group_{ik}$ = indicator variable for group allocation of the YP's YPSW and SSW (0=control; 1=intervention) within LA k ;

X_{ik} = baseline externalising score for young person i within LA k ;

LA_k = a vector for the local authority dummy variables, of which there will be seven. β_3 is a coefficient vector for the LA dummy covariates;

ε_{ik} = residual error term.

Secondary outcome analysis

There are a range of secondary outcome measures reflecting the fact that the Theory of Change suggests that impacts should be observed for all the groups potentially affected by the SW training, namely YP, FCs, and the social workers themselves.

1. Young people

There are six secondary outcomes for YP:

- The SDQ internalising score (continuous variable);
- The SDQ prosocial score (continuous variable);

and four outcomes taken from SSSA903 data:

- One or more unplanned moves (binary);

- Transition into residential care (binary);
- Conviction or subject to youth caution (binary);
- Any missing from care episodes (binary).

2. Foster carers

There are four secondary outcomes for foster carers (detailed in the trial protocol):

- The three Professional Quality of Life (ProQOL) subscales (continuous variables):
 - o compassion satisfaction;
 - o burnout;
 - o secondary traumatic stress.
- Knowledge and understanding of TIP score (continuous).

3. Social workers

For social workers in the trial, there is just one secondary outcome:

- ARTIC score (continuous)

The analysis of the secondary outcomes will be conducted following similar overall model specifications as the primary outcome analysis, but with some modifications to reflect the nature of the data. These are:

- The models for the binary outcomes will be logistic regressions rather than linear;
- For the SSDA903 outcomes, for YP just entering foster care there will be no applicable baseline data. To account for this, a baseline outcome will be included in the model coded as categorical: present, absent; not applicable.

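### Eq 4 (four-arm exploratory model) takes a generic outcome but fixes the baseline covariate as the externalising score, against the SAP's own-baseline rule; a minor specification error affecting the young person secondary outcomes

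*SAP*

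**What the plan says.** The SAP section Analysis of all four arms of the trial sets the scope: "An exploratory analysis for the primary and secondary outcomes will include Analysis Arms 3 and 4 in the regression model". It gives one model, Eq 4. There Y is the "outcome score at follow-up for young person i assigned at baseline to YPSW j within LA k", so it is not tied to one scale, but X is the "baseline externalising score for young person i assigned at baseline to YPSW j within LA k". The remaining terms are the two allocation indicators, their interaction, the LA dummies, the YPSW random effect and the residual. Nothing in that section lets X change with the outcome.

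Elsewhere the SAP states a different rule. The opening of the Analysis section describes the impact model for each outcome "with the baseline version of each outcome being entered as a covariate". Under Secondary outcome analysis, the binary outcomes get logistic models, and for the SSDA903 outcomes "a baseline outcome will be included in the model coded as categorical: present, absent; not applicable". Table 1 (Trial design) lists the baseline sources for the secondary outcomes, including the carer-reported SDQ and, from administrative data, "unplanned moves (SSDA903 2023-2024); missing from care episodes (SSDA903 2023-2024".

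**The concern.** Eq 4 is an operative model definition, and it conflicts with the general rule for every young person outcome except the primary one. An analyst who follows the equation enters baseline externalising for SDQ internalising or prosocial. An analyst who follows the Analysis section enters the outcome's own baseline. The SAP does not say which governs, and it states that the analyst will not be blind to allocation.

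The covariate matters more here than in the two-arm comparison. The SAP describes Arms 1 and 2 as balanced, so there own-baseline adjustment mainly adds precision. For the four-arm model it says: "Given that Arms 3 and 4 are not balanced with Arms 1 and 2", and it warns that the effects may be biased. Leaving out the own baseline gives up precision and also leaves any own-baseline difference between those pairs of arms in the estimates.

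For the SSDA903 outcomes there is a further consequence. The SAP expects close to complete administrative data for young people who stay in foster care, but the externalising baseline comes from the carer survey, which has substantial non-response.

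**Working it through.** **1. The definitions side by side.**

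| Place in SAP | Outcome Y | Baseline covariate |
|---|---|---|
| Analysis, opening rule | each outcome | baseline version of that outcome |
| Eq 1 and Eq 2 | externalising | externalising (own baseline) |
| Secondary outcome analysis, SSDA903 | four binary outcomes, logistic | own baseline in three categories |
| Eq 4 | generic outcome score | externalising only |

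Eq 1 and Eq 2 are consistent because Y is externalising there. In Eq 4, Y was generalised and X was not. The list of terms under Eq 4 also still gives β3 as the LA coefficient vector, although in Eq 4 β3 multiplies the interaction and β5 the LA dummies. Both features suggest that Eq 1's definitions were carried over without full revision.

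**2. The SAP's own figure.** Inputs from Sample size calculations overview: n1 = 183, n2 = 208, m = 1.5, ICC = 0.2, R = 0.6.

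MDES = 2.80 × √[(1/183 + 1/208) × (1 + 0.5 × 0.2) × (1 − 0.36)] = 0.238, against the stated 0.24. With R = 0.53 it is 0.252, against the stated 0.25. The SAP's formula reproduces. Its dependence on the covariate is through the factor (1 − R²).

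**3. Precision.** Let R be the correlation of follow-up with the outcome's own baseline and r its correlation with baseline externalising. The SAP gives 0.6 and 0.53 for externalising and SDQ scores and nothing for the other scales, so R and r are both assumptions here.

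SE ratio = √[(1 − r²)/(1 − R²)]

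- R = 0.6, r = 0: √(1/0.64) = 1.25
- R = 0.6, r = 0.4: √(0.84/0.64) = 1.15
- R = 0.53, r = 0: √(1/0.7191) = 1.18
- R = 0.53, r = 0.4: √(0.84/0.7191) = 1.08

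Standard errors are therefore about 15% to 25% larger at R = 0.6, and 8% to 18% larger at R = 0.53. The SAP expects low correlations for the non-SDQ SSDA903 outcomes, so the loss there would be smaller. The formula is for linear models and is only a guide for binary outcomes.

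**4. Where own-baseline differences go.** With 0/1 coding (Z1 for the YPSW, Z2 for the SSW):

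- β1 = Arm 4 − Arm 2
- β2 = Arm 3 − Arm 2
- β3 = Arm 1 + Arm 2 − Arm 3 − Arm 4

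β1 and β2 each cross the line between the unbalanced pairs. Suppose Arms 3 and 4 share an own-baseline difference d from Arms 1 and 2 that externalising does not capture, and the slope on own baseline is b. Then b × d stays in β1 and in β2, and −2 × b × d in β3. Illustration with b = 0.6 and d = 0.1 sd (both assumed): 0.06 sd in each single-worker effect and −0.12 sd in the interaction. The SAP gives no value for d.

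**5. Sample for the SSDA903 outcomes.** Carer-survey baseline data exist for 558 of the 979 young people in the primary arms: 558/979 = 57%. A complete-case fit with baseline externalising as the covariate would drop the rest. The three-category baseline does not depend on the carer survey. If 57% also held in Arms 3 and 4 (assumption), about 1,477 × 0.43 = 635 of the 1,477 eligible young people would be lost.

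**The case against.** The strongest reply is that this is a drafting slip which the rest of the SAP resolves. The general rule opens the Analysis section, the SSDA903 baseline is set out separately, and the stale β3 label shows that the definitions were copied. An analyst reading the whole document would probably enter the own baseline. The analysis is also exploratory: the SAP does not expect significance, presents the results descriptively, and undertakes to explain that they may be biased.

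Most of that stands, and it limits the severity. It does not remove the point: the slip is in the model definition itself, and no sentence in the four-arm section says that X follows the outcome.

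A reader might infer more than the document supports:

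- **Foster carer and social worker outcomes.** Eq 4 is indexed by young person, so it does not fit those outcomes as written. Saying that the ProQOL, carer knowledge or ARTIC models would use baseline externalising is extrapolation.
- **Loss of power from 80%.** The SAP claims no power for the Eq 4 contrasts, so there is no 80% to fall from.
- **A known bias.** The SAP describes Arms 3 and 4 as differing in experience, with YPSWs and SSWs who work together infrequently. It reports no difference in baseline scores. The bias figures in the working show how a difference would carry through; they are not an estimate of one.
- **A cure for the imbalance.** Own-baseline adjustment would reduce the imbalance that the SAP describes but would not remove it.

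**Conclusion.** The inconsistency is real and minor. Eq 4, as written, gives the young person secondary outcomes the wrong baseline covariate, contrary to the SAP's own rule. The clearest cases are SDQ internalising and prosocial, which are continuous and fit Eq 4 directly. The four SSDA903 outcomes are binary, so the linear form does not suit them either.

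The precision cost for the continuous scales is about 15% to 25% on the standard error, resting on the assumed correlations of 0.6 and 0 to 0.4. For the SSDA903 outcomes the precision cost through the covariate is smaller, and the possible restriction to carers who responded at baseline matters more. The size of any own-baseline difference left in the single-worker and interaction estimates cannot be determined from the document. The primary outcome in Eq 4 already has its own baseline, and no two-arm analysis is affected.

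**What to change.** In the terms under Eq 4:

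1. Define X as the baseline value of the outcome being analysed, for the young person assigned at baseline to YPSW j within LA k.
2. State that the four SSDA903 outcomes use the logistic form and the present, absent or not applicable baseline already set out under Secondary outcome analysis.
3. Relabel the LA coefficient vector as β5.

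Baseline externalising may stay as an additional covariate for the SDQ scales, but not in place of the own baseline. Keep the existing caveats about imbalance. The cost is a few lines of SAP wording; the baselines are already listed in Table 1, so no new data or participants are needed.
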